11.1.1.7 Dose

The total dose of CETO (comprising both [¹⁸F]-labelled and naturally occurring unlabeled CETO) in a single bolus will not exceed 10 micrograms. This takes into account the microdosing toxicology study performed in rats, where a dose 1000 times the dose of the planned participant dose was investigated. The dose showed no toxicologic findings in rats. The expectation is that a dose of 1/1000 of this can therefore safely be given to humans without any expected toxicologic effect and the safety margin should be sufficient to account for potential species differences between rats and humans.

11.1.1.8 Administration

Since the [¹⁸F]CETO vials could contain more radioactivity than is required for 1 subject dose at the time of administration, the correct volume will be calculated prior to administration. The injectable volume of [¹⁸F]CETO will be determined by the PET-CT radiographer, based on the concentration (MBq/ml) provided by WBIC Radioipharmaceutical Unit. Where multiple participants will be dosed on a given day, calculation and preparation of each consecutive dose can only be done once the previous dose has been administered. [¹⁸F]CETO calculated volume will be injected intravenously immediately prior to scan commencement by a trained radiographer. This will be followed by administration of 0.9% Saline flush, up to a volume of 10ml using a syringe. The administration site will be evaluated pre- and post administration for any reaction (e.g. bleeding, hematoma, redness, or infection.

Aseptic conditions must be observed during withdrawal of a dose from the vial, including microbial decontamination of the rubber stopper with a suitable disinfectant before removal of a dose.

11.1.1.9 Known drug reactions

There are no expected drug reactions to [18F]CETO administration.

11.1.1.10 Known drug interactions and concomitant medications

There are no expected drug interactions for [¹⁸F]CETO. Therefore, continuation of pre-existing concomitant medications for patients is permitted. Concomitant medications at the point of [¹⁸F]CETO administration are not permitted for healthy volunteers. Administration of medication to treat adverse events following [¹⁸F]CETO administration is permitted.

11.1.1.11 Dose modifications

No dose modifications will be made to the dose of [18F]CETO.

11.2 Accountability and dispensing

11.2.1 PET-CT responsibilities

IMP for the trial will be ordered in accordance with the usual clinical process for the CUH PET-CT centre. Documentation of the IMP administered to a subject will be recorded on the appropriate CRF, including date, batch number, total volume, total radioactivity, start/stop time of administration, and injection site. This will be undertaken by a suitably qualified member of the PET-CT unit. Drug accountability IMP accountability will be maintained by the WBIC Radiopharmaceutical Unit in accordance with their SOP(s).

Treatment compliance:

Subjects will receive[¹⁸F]CETO Injection under direct supervision of study personnel. Each administration volume and total radioactivity injected should be checked. The label on the IMP container should include the batch number, expiry date/time activity in MBq, time of activity measurement, and volume. The volume per administration should be recorded in each participant's source document and CRF.

11.2.2 Returns and destruction

After decay, the IMP will be returned to the WBIC for disposal. IMP destruction will be performed by the WBIC Radiopharmaceutical Unit in accordance with existing unit SOP(s). Waste must be disposed of according to national regulations for radioactive material.

12 Procedures and assessments

All procedures and assessments will be carried out at CUH.

12.1 Participant identification

Healthy volunteers will be recruited using the approved CETO Healthy Volunteer Poster or through word of mouth. Patients will be identified from the endocrine clinic at CUH and from endocrine referrals received by neighbouring trusts as per routine standard clinical practice.

12.2 Consent

The Informed Consent Form must be approved by the Research Ethics Committee (REC) and must be in compliance with GCP, local regulatory requirements and legal requirements. The investigator or designee must ensure that each trial participant is fully informed about the nature and objectives of the trial and possible risks associated with their participation.

The investigator or designee will obtain written informed consent from each participant before any trial-specific activity is performed. The informed consent form used for this trial and any change made during the course of this trial, must be prospectively approved by the REC. The investigator will retain the original of each participant-signed informed consent form. Written informed consent will be sought at least 24 hours following the participant being in receipt of the Participant Information Sheet.

Should a participant require a verbal translation of the trial documentation by a locally approved interpreter/translator, it is the responsibility of the individual investigator to use locally approved translators.

Any new information which becomes available, which might affect the participant's willingness to continue participating in the trial, will be communicated to the participant as soon as possible.

12.3 Screening evaluation

12.3.1 Screening Assessment

Trial-specific assessments will only be conducted after participants have had all of their questions answered and have provided written informed consent.

The following will be undertaken at the screening assessment:

- Photo ID check
- Medical history (including medications) and
- Physical examination

- 12-Lead ECG
- Pregnancy test (serum hCG) in females of child-bearing potential
- Blood tests:
 - full blood count (FBC) (haemoglobin, white cell count, platelet count)
 - urea & electrolytes including creatinine (U&Es), bicarbonate
 - liver function tests (LFTs) [bilirubin, alanine transaminase (ALT), alkaline phosphatase (ALP)]
 - short synacthen test (SST)
- Urine tests:
 - drugs of abuse point of care screen (amphetamine, barbiturates, benzodiazepine cocaine, marijuana, MDMA, metamphetamine, methadone, morphine, tricyclic antidepressants),
- Inclusion/exclusion criteria review

Data from the screening visit, in conjunction with review of the inclusion/exclusion criteria, will be medically reviewed before confirmation of participant eligibility to proceed to a baseline visit and PET-CT scan.

Time will be dedicated to answer any further participant queries regarding the trial. Information regarding what to expect on the scan day will be provided to the participant. All participants will be advised of the need to fast for a minimum of 4 hours before the [18F]CETO injection on the PET-CT scan date.

Following the screening visit, a member of the trial team will contact the participant's GP to verify their eligibility to be enrolled in the trial. Confirmation of the participant's relevant past medical and surgical history, current medications, recreational drug use, alcohol consumption, previous clinical trial involvement and previous radiation exposure will be verified with the GP. Written communication verifying participant eligibility will be sought from the participant's GP prior to proceeding to the baseline visit and PET-CT scan..

All healthy volunteers will be registered on The Over-Volunteering Prevention System (TOPS) database (which is available via the CLRF), and any existing record of participants on the database will be reviewed prior to confirming their eligibility for this trial.

On verification of eligibility, participants will be informed of their successful recruitment onto the trial by a member of the research team. A baseline visit will then be booked with the participant.

12.3.2 Participant Registration/Randomisation

All consenting participants will be provided with a unique participant ID number at their screening visit which will be used on all trial documentation and will be added to the CRF following consent. Participants who subsequently pass screening will retain their participant ID throughout the trial which will be included on the CRF.

12.3.3 Intensive Care Unit (ICU)

The ICU team will be provided with details of the study prior to its commencement. In the days preceding admission of trial participants to the CLRF, the ICU team will be provided with details of the impending admission. Evidence of notification will be retained.

12.4 Baseline Assessments

Baseline assessments are scheduled to occur on the day of the PET-CT scan and will occur a minimum of 1 week after the screening visit. Participants will require a minimum 4 hour fast before the PET-CT scan, however water is permitted during this fasting period. On completion of the PET-CT scan, participants will be permitted to eat and drink as normal, with no restrictions.

Photo ID will be reviewed by a member of the clinical research team to confirm participant identity prior to dosing.

Baseline activities will include:

- Confirmation of continued willingness and eligibility to participate in the study
- Update to medical history (including current medication) and physical examination
- Recording of participant demographics
- Repeat 12-lead ECG
- Pregnancy test (to confirm the negative result from the screening visit, a rapid turnaround urine hCG assay will be used) in females of child-bearing potential
- Insertion of intravenous cannula
- Blood tests:
 - FBC
 - U&Es, bicarbonate
 - LFTs
 - Direct Renin Concentration (DRC)
 - Plasma Aldosterone Concentration (PAC)
 - Adrenocorticotropic Hormone (ACTH)

12.5 Trial assessments

IMP Administration & PET-CT

Healthy volunteers and patients will attend the PET-CT unit at CUH. Recruitment of healthy volunteers and patients will occur concurrently (i.e. it will not be necessary for all healthy volunteers to be recruited before patients will be recruited). All scans will be performed on a GE Discovery PET-CT scanner. During the [¹⁸F]CETO injection and the PET-CT scan, a clinical research fellow and research nurse will supervise the participant. We will perform sentinel dosing for the first overall IMP dose on the trial. Specifically, only a single participant will receive the IMP and proceed through the trial before any subsequent participants are administered with the IMP. The Principal Investigator will be present during the first injection of [¹⁸F]CETO in the first participant. For subsequent injections, the Principal Investigator will be contactable by the unit in the unlikely event of an emergency. Details of the emergency equipment and processes for the PET-CT Unit can be found in section 13 Toxicity - Emergency Procedures.

A detailed description of the IMP administration and PET-CT scan process is described below:

- Participants will be asked to void their bladder before the PET-CT scan
- A positioning attenuation correction (CTAC) scan will be performed.
- Participants will then receive a 2MBq/kg IV injection of [¹⁸F]CETO, up to a maximum of 200 MBq. The radiotracer will be injected over approximately 30 seconds.
- A dynamic PET scan will occur immediately following the injection of [¹⁸F]CETO and will last for 90 minutes from the point of injection. Dynamic scanning will be performed to provide information on the optimum image acquisition window.
- List-mode PET data acquisition will last for the duration of imaging and facilitate the creation of retrospective static and dynamic images needed for optimisation.
- Pulse oximetry will be acquired and recorded throughout imaging.
- At the end of the scan participants will be asked to void their bladder and drink water ad libitum as this promotes the removal of radioactive material from the body
- Vital signs will be measured, and a 12-lead ECG will be performed after the scan

In the unlikely event of a failure of tracer production (with no ability to rectify on the day in question), participants will be rescheduled for a PET-CT scan on a separate date.

Period of Observation

Following the IMP administration and PET-CT scan, the following will occur:

After completion of the scan, participants will remain in the PET-CT unit for up to 4 hours following injection of the radiotracer. They will be accompanied throughout this time by a trial research nurse and members of the PET-CT team, and will be reviewed on a regular basis by a clinical research fellow or the Principal Investigator. The unit is a fully accredited NHS PET facility and is fully equipped to deal with any adverse event following [18F]CETO administration.

- Vital signs will be checked at approximately 30 minute intervals throughout this time.
- Participants will subsequently be accompanied to the CLRF (which lies on the same corridor as the PET-CT unit) by the clinical research fellow and research nurse, where they will be observed in the Early Phase Unit of the Clinical Research Facility (CLRF) until approximately 24 hours following injection of [18F]CETO.
- On arrival at the CLRF, vital signs will be checked and repeated when clinically
 indicated thereafter. A clinical member of the research team will be available for
 advice from the baseline visit up to the point of participant discharge from the
 CLRF. They will be able to attend the CLRF to review the participant within
 approximately 10 minutes of a request for clinical review.
- In the unlikely event that the participant acutely deteriorates, a CUH rapid response team will attend the CLRF and make a decision regarding transfer to the main hospital. The Early Phase unit is on Level 3 of the CLRF, with a link

corridor to allow direct access to the main hospital. It will take approximately 2 minutes for participants to be transferred to the intensive care unit in the rare instance that this situation was to arise.

The following morning, participants will have repeat blood tests including a short synacthen test (SST) to evaluate adrenal function. Although the doses of [18F]CETO administered in humans will be significantly lower than used in the rat microdosing studies, and it is therefore very unlikely that clinically relevant short-term adrenal suppression will occur, we have included a SST following injection of the radiotracer to provide reassurance that adrenal function remains normal in participants. Following review of the results by a clinical member of the research team, participants will be discharged from the CLRF. In the unlikely event that a participant returns an abnormal SST result, they will be reviewed by a member of the clinical research team and the decision will be taken as to whether they temporarily need low dose hydrocortisone treatment until the test is repeated one week later.

Dexamethasone Prescription (Patients only)

Prior to discharge from the CLRF and where SST results were confirmed to be acceptable, patients will be provided with a prescription for dexamethasone 500 micrograms four times daily for three days (total 12 doses). Dexamethasone will be self-administered for three days (total 12 doses) prior to the repeat PET-CT scan. Patients will be provided with contact details for the research team if they have any questions while taking dexamethasone. The purpose of this pre-treatment with dexamethasone will be to improve the ability to distinguish between abnormal and normal adrenal tissue in the subsequent scan. Therefore, a second scan with dexamethasone pre-treatment will only be required for patients and not healthy volunteers.

Follow up visit for those with abnormal synacthen test result

Any individuals with an abnormal SST approximately 24 hours post injection of [18F]CETO will be invited to a follow-up visit at 7 (+/-2 days) for a repeat test. At that visit, the participant will also be assessed by a clinical member of the research team. A repeat SST will be conducted during this visit, and the results assessed by the clinical research fellow and, if clinically indicated (for example if a further abnormal result is returned), by the Principal Investigator before the participant goes home.

In the extremely unlikely event that the abnormality persists, the participant will continue to be monitored within the trial until one of the following conditions is met:

- Adrenal function returns to baseline, as determined by follow-up SST.
- Participant/patient remains clinically stable, and where further follow-up can be managed safely in the outpatient setting.
- An alternative cause for the adrenal dysfunction is identified.
- Participant/patient is lost to follow-up.

Upon which their involvement in the trial will end.

Repeat PET-CT (Patients only)

Any patient who had an abnormal short synacthen test following the first scan will not be eligible to undergo the second scan. Eligible patients will undergo a second PET-CT scan (with dexamethasone pre-treatment) at ≥7 days after the initial scan

Prior to undertaking the second scan, the following assessments will be performed:

- Photo ID check
- Review of Dexamethasone medication diary
- Repeat urine pregnancy test for women of childbearing potential
- Blood tests:
 - FBC
 - U&Es, bicarbonate
 - LFTs
 - Direct Renin Concentration (DRC)
 - Plasma Aldosterone Concentration (PAC)
 - Adrenocorticotropic Hormone

Patients who fail to demonstrate 100% self-administration of dexamethasone in accordance with instructions provided by the trial team, assessed by review of the Dexamethasone medication diary, will not be able to proceed to a repeat PET-CT scan.

As no abnormal findings were recorded for these patients following the first scan, patients will only be observed for up to 4 hours in the PET-CT Unit after completion of the second scan. They will then be discharged by a clinical member of the research team with no requirement for admission to the CLRF or an additional SST.

Ongoing Safety Review

The safety data and PET-CT data will be reviewed by the Data Monitoring Committee (DMC) following injections of [¹⁸F]CETO in the first 3 participants to provide an initial evaluation of [¹⁸F]CETO safety and confirm the trial is able to proceed.

Furthermore, automatic trial stopping criteria will be met if a single participant experiences any serious adverse reaction (SAR, i.e. a serious adverse event considered at least possibly related to the IMP administration). Stopping criteria will additionally apply if any severe non-serious adverse reactions (ARs) develop in two participants, independent of whether or not these are within the same system-organ-class. The following will then occur:

- The trial will be halted via a substantial amendment to the MHRA.
- No further dosing or recruitment will be undertaken
- A safety review by the Data Monitoring Committee (DMC) will be conducted to determine how to proceed with the trial
- Any patients who have their dosing discontinued as a result of a SAR or a severe nonserious AR will be withdrawn from the trial
- Re-initiation of the trial can only be considered after MHRA approval via a substantial amendment. Any concurrently active participants will be re-consented before further IMP doses are administered, and all completed participants will be informed of the SAR or severe non-serious ARs.

12.6 Schedule of Assessments

Assessment	Screening	Baseline	[¹⁸ F]CETO PET-CT Scan Day (Volunteers)	Morning following Scan (Volunteers)	[¹⁸ F]CETO PET-CT Scan Day (Patients)	Morning following Scan (Patients)	SST Follow- up Visit (Volunteers & Patients) – if necessary	Repeat [18F]CETO PET-CT Scan Day (Patients)
Visit	1	2 ^b	3 ^b	3 ^b	3 ^b	3 ^b	4	5
Informed consent	Х							
Eligibility assessments	X							
Medical history	Х	Х					Х	X
Physical	X	Χ					X	
Vital signs only			X	X	X	X		X
Demographics		Χ						
Bloods & Urine								
FBC	X	X		X X X		X	X X X	X X X
U&Es	X	Χ		X		X X	X	X
LFTs	X X X	Χ		X		X	X	X
Serum HCG ^a	X							
Urine HCG ^a		X						X
DRC		X						X X X X
PAC		X						X
ACTH		X						X
Bicarbonate	X	X		V		V	V	X
SST	X			X		Х	X	
Drugs of abuse	X							
ECG	Х	Х	X		X			X
Adverse event			Х		Х		X	Х
assessments								
Photo ID Check	X		X		X			X

EudraCT Number: 2018-004851-18 IRAS ID: 248713 Page 39 of 52

Assessment	Screening	Baseline	[¹⁸ F]CETO PET-CT Scan Day (Volunteers)	Morning following Scan (Volunteers)	[18F]CETO PET-CT Scan Day (Patients)	Morning following Scan (Patients)	SST Follow- up Visit (Volunteers & Patients) – if necessary	Repeat [18F]CETO PET-CT Scan Day (Patients)
IMP administration			X		X		,	X
Dexamethasone pre-								Х
treatment								

Key:

Abbreviations: ACTH Adrenocorticotrophic Hormone; DRC, Direct Renin Concentration; ECG, Electrocardiogram; FBC, Full Blood Count; HCG, Human Chorionic Gonadotrophin; IMP, Investigational Medicinal Product; LFTs, Liver Function Tests; PAC, Plasma Aldosterone Concentration; SST Short Synacthen Test; U&Es, Urea & Electrolytes.

^aFemales of child-bearing potential.

^bVisits 2 and 3 will occur over two consecutive days

12.7 End of Trial Participation

Healthy volunteers will conclude their involvement in the trial after their final adrenal function assessment has confirmed normal adrenal function or they are transitioned to clinical care as a patient following a confirmed abnormal result.

Patients will conclude their involvement in the trial after the second [¹⁸F]CETO PET-CT scan or, in the event of an abnormal result following the first scan, after their final adrenal function assessment has confirmed normal adrenal function. Participants who continue to be monitored within the trial until one of the following conditions is met:

- Adrenal function returns to baseline, as determined by follow-up SST.
- Participant/patient remains clinically stable, and where further follow-up can be managed safely in the outpatient setting.
- An alternative cause for the adrenal dysfunction is identified.
- Participant/patient is lost to follow-up.

Upon which their involvement in the trial will end.

Healthy volunteers will not receive routine follow up after the trial. Patients will be returned to their normal clinical care.

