9.6 Trial Outcome Measures

9.6.1 Primary outcome Measure

• The primary outcome measure is the overall safety of [¹⁸F]CETO. This will be assessed according to the frequency of adverse events, serious adverse events, clinically significant changes in vital signs, ECG and laboratory parameters.

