12.8 Trial restrictions

Women of childbearing potential will be required to use highly effective contraception for the duration of the trial and for 7 days after the completion of the last scan. This includes:

- Intrauterine Device (IUD)
- Oral contraceptive (progestogen alone note combined oral contraceptives containing oestrogen and progesterone are not permitted). Progesterone-only hormonal contraception preparations are only considered acceptable if the main mechanism of action is inhibition of ovulation.
- True abstinence (where this is in accordance with the participants preferred and usual lifestyle)

Men will be required to use adequate contraception for the entire duration of the trial and for 7 days after completion of the last scan.

- Barrier contraception (condom and occlusive cap e.g. diaphragm or cervical cap with spermicide)
- True abstinence (where this is in accordance with the participants preferred and usual lifestyle)

13 Assessment of Safety

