13.1 Definitions

13.1.1 Adverse event (AE)

Any untoward medical occurrence in a participant or clinical trial participant administered a medicinal product and which does not necessarily have a causal relationship with this treatment.

An adverse event can therefore be any unfavourable and unintended sign (including an abnormal laboratory finding), symptom, or disease temporally associated with the use of an investigational medicinal product, whether or not considered related to the investigational medicinal product.

Please note: Recording of all adverse events must start from the point of Informed Consent regardless of whether a participant has yet received a medicinal product.

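### Adverse-event recording has a start but no stated end, and the collection windows implied by the visits run from about 5.5 hours to at least 7 days after an injection

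*Protocol*

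**What the plan says.** Section 9.6.1 defines the primary outcome as overall safety: "This will be assessed according to the frequency of adverse events, serious adverse events, clinically significant changes in vital signs, ECG and laboratory parameters". It attaches no time window.

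Section 13.1.1 fixes the start of recording: "Recording of all adverse events must start from the point of Informed Consent regardless of whether a participant has yet received a medicinal product". Section 13.4 repeats this. Neither these nor any other section gives an end.

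The end can only be read from the visit structure:

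- **Volunteers.** Section 12.5 keeps all participants under observation until about 24 hours after the first injection, with an SST that morning. Under section 12.7 a volunteer's participation ends once adrenal function is confirmed normal, and "Healthy volunteers will not receive routine follow up after the trial".
- **Patients, first dose.** With a normal SST, the next visit is the repeat scan, 7 or more days after the first. Three days of self-administered dexamethasone fall in that interval (12.5).
- **Patients, second dose.** Section 12.5 states that "patients will only be observed for up to 4 hours in the PET-CT Unit after completion of the second scan". Participation then ends (12.7).
- **Abnormal SST, either group.** There is a follow-up visit at 7 (+/-2) days, and patients have no second scan (12.5).

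In the schedule (12.6), the AE row is marked on the scan days, at the conditional SST visit and on the repeat scan day. It is blank at screening, at baseline and in both columns for the morning after the scan.

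**The concern.** A count of adverse events means little without the period over which events were sought. Here that period is undefined at its far end, and the visits imply very different lengths for volunteers, first doses in patients and second doses in patients.

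Two things follow. First, an event that begins after discharge in a volunteer, or after a second dose, has no scheduled route into the primary outcome. Nor does it have one into the stopping rule, which counts one serious adverse reaction, or severe non-serious reactions in two participants (12.5, 16.4). The primary objective covers up to two administrations (9.5.1), and the second is the one with the shortest collection. Second, if AE frequencies are pooled or tabulated side by side, the patients' first dose will tend to show more events simply because it is watched for longer, partly while another drug is being taken.

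The AE row in 12.6 also does not match 13.1.1: recording is required from consent, but no AE assessment is marked before the scan day.

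**Working it through.** The protocol has no power calculation (16.1), so there is no figure of its own to reproduce. The check is arithmetic on its stated times.

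**Inputs.** Up to 5 volunteers and 6 patients (16.3). Scan of 90 minutes from injection, and first-dose observation to about 24 hours (12.5). Repeat scan at 7 days or later (12.5). Up to 4 hours after the second scan is completed (12.5).

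**Administrations.** 5 + 6 × 2 = 17.

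**Second-dose window.** 1.5 h + 4 h = 5.5 h; 5.5/24 = 0.229 day. Section 9.4 gives a 4-hour period without saying whether it runs from injection or from the end of the scan. If from injection, it is 4/24 = 0.167 day.

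**Implied windows, normal SST:**

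| Administration | Number | Window (days) | Person-days |
|---|---|---|---|
| Volunteers, single dose | 5 | about 1 | 5 |
| Patients, first dose | 6 | at least 7 | at least 42 |
| Patients, second dose | 6 | 0.229 (0.167 on the 4 h reading) | 1.4 (1.0) |

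The total is about 48 person-days. The first-dose window in patients is 7/1 = 7 times that in volunteers, and 7/0.229 = 30.5 times the second-dose window (7/0.167 = 42 on the shorter reading). Administrations with about a day or less: 5 + 6 = 11 of 17. Under 6 hours: 6 of 17.

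**How many dose-related events would be caught?** The protocol gives no onset time. As an assumption, let onset be exponential with mean m days, so that the share caught in a window t is 1 − exp(−t/m):

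| Assumed mean onset m | Volunteers | Patients, dose 1 | Patients, dose 2 (4 h reading) |
|---|---|---|---|
| 0.1 day | 100% | 100% | 90% (81%) |
| 1 day | 63% | 100% | 20% (15%) |
| 3 days | 28% | 90% | 7% (5%) |

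**Effect of unequal time at risk.** As a second assumption, take the same constant background AE rate for everyone and no tracer effect. The chance of at least one counted AE is 1 − exp(−rate × t):

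| Assumed rate per day | Volunteer | Patient, dose 1 | Patient, dose 2 (5.5 h) |
|---|---|---|---|
| 0.01 | 1.0% | 6.8% | 0.2% |
| 0.05 | 4.9% | 29.5% | 1.1% |
| 0.1 | 9.5% | 50.3% | 2.3% |

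The rates are illustrative. Identical true risk gives quite different crude frequencies throughout the range.

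**Against a common window.** With 7 days after every administration (an illustrative reference), the total would be 17 × 7 = 119 person-days. The plan as written covers 48.4/119 = 41% of that (48.0/119 = 40% on the 4 h reading).

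**The case against.** Several points on the other side carry weight.

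- **No comparison is planned.** Section 16.1 promises only summary statistics for the monitoring committee, and the volunteer-versus-patient comparison in section 15 concerns tracer uptake. A reader might infer that an AE comparison is invalid. The documents contain none, so no stated analysis fails. The difficulty is in interpreting the counts and in their completeness.
- **Under-counting is not shown.** A reader might infer that events are being missed. That holds only if reactions are delayed. Sections 7.2 and 11.1.1.7 report rapid metabolism in animals and a dose cap of 10 micrograms, and neither points to late effects. But onset in humans is unknown in a first-in-human trial, so the risk remains.
- **The shorter second stay is explained.** Sections 9.4 and 12.5 rest it on tolerance and normal results after the first dose. That is a reason for not keeping patients overnight. It does not bear on whether anyone asks about events afterwards.
- **The schedule can be read more kindly.** The scan day and the following morning are both Visit 3, so one AE mark may cover both. Participants are still under observation, with vital signs, bloods and a clinical review of results, and medical history is updated at baseline. Recording could therefore run continuously despite the blank cells. This softens the mismatch with 13.1.1 but leaves the post-discharge gap untouched.
- **The windows are not universal.** Participants with an abnormal SST are seen at day 5 to 9 and possibly later.
- **Contraception.** A reader might take the period in 12.8, "for the duration of the trial and for 7 days after the completion of the last scan", as the protocol's own AE window. It is not presented as one, and section 13.7 uses 1 month for pregnancy notification by participants. Neither period defines AE collection.
- **Follow-up of volunteers.** The sentence in 12.7 about no routine follow-up concerns the time after the trial and does not itself set an AE window. The stronger evidence is 12.5, the AE row in 12.6, and 13.1.1.

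Reporting windows and denominators could be left to an analysis plan. Collection could not: an analysis plan cannot recover events that nobody asked about.

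**Conclusion.** The point stands as a defect in data collection for the primary outcome. AE recording has a stated start and no stated end. For participants with a normal SST, the implied windows are about 24 hours (volunteers), at least 7 days (patients, first dose) and about 5.5 hours from injection (patients, second dose). Eleven of 17 planned administrations have about a day or less, and 6 have under 6 hours.

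These windows are inferred from visits and end of participation, and assume full recruitment, normal SSTs and all second scans performed. The ratios of 7 and about 30 follow from the protocol's times. The number of events lost does not: it depends on assumed onset, and for second doses ranges from a loss of about 10% at a mean onset of 0.1 day to about 93% at 3 days (5.5 h reading). Crude frequencies would mix unequal time at risk, but the documents do not support saying that a planned comparison is invalid or that events are certainly under-counted. The change is worth making before recruitment because it is cheap and cannot be made good afterwards.

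**What to change.** 1. State one common end point for AE collection after every administration. Close it with a scheduled telephone enquiry for volunteers and after the second dose. The length is for the sponsor to set and justify; 7 days would match the shortest interval between doses in patients, so their first-dose window could be reported on the same footing.
2. Align the AE row in 12.6 with 13.1.1 by marking screening, baseline and both morning-after-scan columns.
3. Report AEs per administration within the same window, with the denominator (up to 11 first and 6 second doses) and time at risk. Identify events that began during dexamethasone.
4. Reconcile the 4-hour period in 9.4 with that in 12.5 by stating whether it runs from injection or from the end of the scan.

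The cost is up to 11 telephone calls (5 volunteers and 6 patients), some schedule wording, and slightly longer participation with no extra visit.
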